8.2 Acquired TTP	

Definition: A disorder characterized by the presence of microangiopathic hemolytic anemia, thrombocytopenic purpura, fever, renal abnormalities, and neurologic abnormalities, such as seizures, hemiplegia, and visual disturbances. It is an acute or subacute condition.
	

Diagnostic work-up History with specific questions related to drug exposure (e.g., chemotherapy, sirolimus, tacrolimus, opana ER antibiotics, quinine) Physical examination, peripheral smear ADAMTS13 activity level and inhibitor titer LDH, haptoglobin, reticulocyte count, bilirubin, urinalysis to rule out other causes PT, activated PTT, fibrinogen Blood group and antibody screen, direct antiglobulin test, CMV serology Consider CT/MRI brain, echocardiogram, ECG Viral studies Note: This disorder is usually associated with a severe drop in platelets and hemolysis/anemia precipitously
	
Grading	Management
All grades	
The first step in the management of TTP is a high index of suspicion for the diagnosis and timely recognition; hematology consult should immediately be called, as delay in identification is associated with increased mortality/morbidity.
 
Initially, the patient should be stabilized and any critical organ dysfunction stabilized

G1: Evidence of RBC destruction (schistocytosis) without anemia, renal insufficiency, or thrombocytopenia clinically G2: Evidence of RBC destruction (schistocytosis) without clinical consequence with G2 anemia and thrombocytopenia
	
Hold ICPI and discuss resumption with patient only after taking into account the risks and benefits, noting that there are currently no data to recommend restarting ICPI therapy Hematology consult Administer 0.5-1 mg/kg/d prednisone


G3: Laboratory findings with clinical consequences (G3 thrombocytopenia, anemia, renal insufficiency > 2) G4: Life-threatening consequences (e.g., CNS hemorrhage or thrombosis/embolism or renal failure)
	
For G3: Hold ICPI and discuss resumption with patient only after taking into account the risks and benefits, noting that there are currently no data to recommend restarting ICPI therapy For G4: permanently discontinue ICPI Hematology consult In conjunction with hematology, initiate PEX according to existing guidelines with further PEX dependent on clinical progress Administer methylprednisolone 1 g IV daily for 3 days, with the first dose typically administered immediately after the first PEX May offer rituximab In case of management with rituximab, ICPI treatment will be discontinued

8.0 Hematologic Toxicities	
8.3 Hemolytic uremic syndrome	

Definition: A disorder characterized by a form of thrombotic microangiopathy with renal failure, hemolytic anemia, and severe thrombocytopenia. Signs and symptoms of hemolytic uremic syndrome can include:
 
Bloody diarrhea Decreased urination or blood in the urine Abdominal pain, vomiting, and occasionally fever Pallor Small, unexplained bruises or bleeding from the nose and mouth Fatigue and irritability Confusion or seizures High blood pressure Swelling of the face, hands, feet, or entire body
	

Diagnostic work-up History and physical examination (special consideration for new history of high-risk drugs, hypertension, or cardiac causes) CBC with indices Blood smear morphology. Note that the presence of schistocytes on smear is critical for diagnosis. Serum creatinine ADAMTS13 (to rule out TTP) Homocysteine/methylmalonic acid Complement testing C3, C4, CH50 (complement inhibitory antibodies for suspected familial) Evaluate reticulocyte count and mean corpuscular volume Evaluation of infectious cause, including screening for EBV, CMV, HHV6 Evaluation for nutritional causes of macrocytosis (B12 and folate) Pancreatic enzymes Evaluation for diarrheal causes, shiga toxin, Escherichia coli 0157, etc. Direct antibody test (Coombs test), haptoglobin, LDH, and other etiologies of anemia Evaluation for common drugs causing hemolysis (tacrolimus, cyclosporine, sirolimus, etc.) Evaluation for concurrent confusion
	
Grading	Management

G1-2: Evidence of RBC destruction (schistocytosis) without clinical consequences of anemia, thrombocytopenia Grade 2 G3: Laboratory findings with clinical consequences (e.g., renal insufficiency, petechiae) G4: Life-threatening consequences (e.g., CNS thrombosis/ embolism or renal failure)
	
For G1 and G2: Continue ICPI with close clinical follow-up and laboratory evaluation Supportive care For G3 and G4: Permanently discontinue ICPI Begin therapy with eculizumab therapy 900 mg weekly for four doses, 1,200 mg week 5, then 1,200 mg every 2 weeks Red blood transfusion according to existing guidelines

8.4 Aplastic anemia	

Definition: Condition in which the body stops producing enough new blood cells
	

Diagnostic work-up History and physical examination (close attention to medications, exposure to radiation, toxins, recent viral infections) CBC, smear, reticulocyte count Viral studies, including CMV, HHV6, EBV, parvovirus Nutritional assessments including B12, folate, iron, copper, ceruloplasmin, vitamin D Serum LDH, renal function Work-up for infectious causes Identify marrow hypo/aplasia Bone marrow biopsy and aspirate analysis Peripheral blood analysis, including neutrophil count, proportion of GPI-negative cells by flow for PNH Flow cytometry to evaluate loss of GPI-anchored proteins
	

8.0 Hematologic Toxicities	
Type and screen patient for transfusions and notify blood bank that all transfusions need to be irradiated and filtered	
Grading	Management
G1: Nonsevere, < 0.5 polymorphonuclear cells x 10 ⁹ /L hypocellular marrow, with marrow cellularity < 25%, peripheral platelet count > 20,000, reticulocyte count < 20,000	Hold ICPI and provide growth factor support and close clinical follow-up, and laboratory evaluation Supportive transfusions as per local guidelines
G2: Severe, hypocellular marrow < 25% and two of the following: ANC < 500, peripheral platelet < 20,000, and reticulocyte < 20,000	Hold ICPI and provide growth factor support and close clinical laboratory evaluations daily Administer ATG + cyclosporine; HLA typing and evaluation for bone marrow transplantation if patient is candidate; all blood products should be irradiated and filtered Supportive care with granulocyte colony-stimulating factor may be added in addition
G3-4: Very severe, ANC > 200, platelet count > 20,000, reticulocyte count > 20,000, plus hypocellular marrow > 25%	For G3: Hold ICPI and monitor weekly for improvement; if not resolved, discontinue treatment until AE has reverted to G1 For G4: permanently discontinue ICPI Hematology consult, growth factor support Horse ATG plus cyclosporine If no response, repeat immunosuppression with rabbit ATG plus cyclosporine, cyclophosphamide For refractory patients, consider eltrombopag plus supportive care
8.5 Lymphopenia	
Definition: An abnormally low level of lymphocytes in PB; for adults, counts of < 1,500/mm ³	

Diagnostic work-up
 
History and physical examination (special attention for lymphocyte-depleting therapy such as fludarabine, ATG, corticosteroids, cytotoxic chemotherapy, radiation exposure, etc., as well as history of autoimmune disease, family history of autoimmune disease) Evaluation of nutritional state as cause
 
Spleen size
 
CBC with differential, peripheral smear and reticulocyte counts
 
CXR for evaluation of presence of thymoma
 
Bacterial cultures and evaluation for infection (fungal, viral, bacterial specifically CMV/HIV)
	
Grading	Management
G1-2: 500-1,000 PB lymphocyte count G3: 250-499 PB lymphocyte count G4: < 250 PB lymphocyte count	Continue ICPI for G1 to G2 For G3 single laboratory values out of normal range without any clinical correlates, hold treatment until resolution to G1 For G4, for single laboratory values out of normal range without any clinical correlates, permanent treatment discontinuation is not required. Treatment should be held until the etiology is determined. Permanent treatment discontinuation will only be required, if lymphopenia is considered of immune related in nature, no clear alternative explanation exists for the event, and grade 4 lymphopenia does not resolve within 14 days. If the event is not considered immune related and resolves to G ≤ 1 restarting treatment may be considered. Check CBC weekly for monitoring, initiation of CMV screening Consider holding ICPI

8.0 Hematologic Toxicities	
	Initiate Mycobacterium avium complex prophylaxis and Pneumocystis jirovecii prophylaxis, CMV screening. HIV/hepatitis screening if not already done May consider EBV testing if evidence of lymphadenopathy/hepatitis, fevers, hemolysis consistent with lymphoproliferative disease.
8.6 Immune thrombocytopenia	
Definition: An autoimmune disorder characterized by immunologic destruction of otherwise normal platelets	
Diagnostic work-up History and physical examination (special attention for lymphocyte-depleting therapy, such as fludarabine, ATG, corticosteroids, cytotoxic therapy) Family history of autoimmunity or personal history of autoimmune disease History of viral illness CBC Peripheral blood smear, reticulocyte count Bone marrow evaluation only if abnormalities in the above test results and further investigation is necessary for a diagnosis Patients with newly diagnosed immune thrombocytopenia should undergo testing for HIV, hepatitis C virus, hepatitis B virus, and Helicobacter pylori Direct antigen test should be checked to rule out concurrent Evan syndrome Nutritional evaluation Bone marrow evaluation if other cell lines affected and concern for aplastic anemia	
Grading	Management
G1: Platelet count < 100/ μ L G2: Platelet count < 75/ μ L	Continue ICPI with close clinical follow-up and laboratory evaluation Hold ICPI but monitor for improvement; if not resolved, interrupt treatment until AE has reverted to G1 Administer prednisone 1 mg/kg/d (dosage range, 0.5-2 mg/kg/d) orally for 2-4 weeks after which time this medication should be tapered over 4-6 weeks to the lowest effective dose IVIG may be used in conjunction with corticosteroids if a more-rapid increase in platelet count is required.
G3: Platelet count < 50/ μ L	Hold ICPI but monitor for improvement; if not resolved, interrupt treatment until AE has reverted to G1
G4: Platelet count < 25/ μ L	Permanently discontinue ICPI Hematology consult Prednisone 1-2 mg/kg/d (oral or IV depending on symptoms) If worsening or no improvement, 1-2 mg/kg/d prednisone equivalents and permanently discontinue treatment IVIG used with corticosteroids when a more-rapid increase in platelet count is required If IVIG is used, the dose should initially be 1 g/kg as a one-time dose. This dosage may be repeated if necessary If previous treatment with corticosteroids and/or IVIG unsuccessful, subsequent treatment may include rituximab, thrombopoietin receptor agonists, or more-potent immunosuppression (From American Society of Hematology guideline on immune thrombocytopenia; consult for further details)

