 - a. Adequate hematological function defined by absolute neutrophil count (ANC) $\geq 1.5 \times 10^9/L$, platelet count $\geq 100 \times 10^9/L$, and hemoglobin (Hgb) ≥ 9 g/dL.

- b. Adequate hepatic function defined by a total bilirubin level \leq the upper limit of normal (ULN), aspartate aminotransferase (AST) and alanine aminotransferase (ALT) levels $\leq 1.5 \times$ ULN. For participants with liver involvement in their tumor, AST $\leq 5.0 \times$ ULN, ALT $\leq 5.0 \times$ ULN, and bilirubin $\leq 3.0 \times$ ULN are acceptable.
 - c. Adequate renal function defined by creatinine $\leq 1.5 \times$ ULN or calculated creatinine clearance (CrCL) ≥ 30 mL/min for participant with creatinine $> 1.5 \times$ ULN (glomerular filtration rate can also be used).
 - Note: CrCL should be calculated per institutional standard. If no local guideline is available, CrCL should be calculated using the Cockcroft-Gault Method:
$$\text{CrCL} = ([140 - \text{age}] \times \text{weight [kg]} \times [0.85 \text{ for females only}]) / (72 \times \text{creatinine}).$$
 - d. Adequate coagulation function defined as international normalized ratio (INR) or prothrombin time (PT) $\leq 1.5 \times$ ULN unless the participant is receiving anticoagulant therapy and activated partial thromboplastin time (aPTT) $\leq 1.5 \times$ ULN unless the participant is receiving anticoagulant therapy.
8. Participants with known HIV infections are in general eligible if the following criteria are met ([FDA Guidance on Cancer Clinical Trial Eligibility, March 2019](#)):
- a. If clinically indicated patients must be stable on antiretroviral therapy (ART) for at least 4 weeks and agree to adhere to ART. If not clinically indicated, consult study Medical Monitor.
 - b. Participants with HIV infection should have no evidence of documented multi-drug resistance that would prevent effective ART.
 - c. Have an HIV viral load of < 400 copies/mL at Screening.
 - d. Have CD4+ T-cell (CD4+) counts ≥ 350 cells/ μ L.
 - e. For patients with a history of an AIDS-defining opportunistic infection within the last 12 months, patients may be eligible only after consultation and agreement with the study Medical Monitor.
 - f. If prophylactic antimicrobial drugs are indicated, patient may still be considered eligible upon agreement with the study Medical Monitor.

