1. If a Grade 2 treatment-related TEAE resolves to Grade \leq 1 by the day before the next infusion, study intervention may be continued.
2. If a Grade 2 treatment-related TEAE does not resolve to Grade \leq 1 by the day before the next infusion, but it is manageable and/or not clinically relevant, the Medical Monitor should be consulted to assess if it is clinically reasonable to administer the following infusion.

Note that treatment recommendations regarding continuation, hold, or discontinuation by grade are different depending on the specific toxicity (refer to [Appendix 5](#)). Toxicity grading is assigned based on NCI-CTCAE v5.0.

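### Table A8 prints the immune thrombocytopenia platelet limits 1000-fold too low and reverses all four signs in the aplastic anemia G3-4 row

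*Protocol*

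**What the plan says.** Protocol Appendix 5, Table A8, block 8.6 grades immune thrombocytopenia by platelet count. The limits for G1 to G4 are below 100, 75, 50 and 25, each per microlitre; the last reads "G4: Platelet count < 25" with that unit. The actions are to continue at G1, hold at G2 and G3, and stop permanently at G4.

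Block 8.4 grades aplastic anemia. Its two upper rows read:

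- "G2: Severe, hypocellular marrow < 25% and two of the following: ANC < 500, peripheral platelet < 20,000, and reticulocyte < 20,000"
- "G3-4: Very severe, ANC > 200, platelet count > 20,000, reticulocyte count > 20,000, plus hypocellular marrow > 25" percent

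G2 leads to a hold. The joint G3-4 row leads to a hold at G3 and a permanent stop at G4.

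Section 6.9.2 and the introduction to Appendix 5 both make the permanent stop mandatory at Grade 4 of these two events. Section 6.8 assigns toxicity grades by NCI-CTCAE v5.0, and it sends the reader to Appendix 5 for the action: "Note that treatment recommendations regarding continuation, hold, or discontinuation by grade are different depending on the specific toxicity".

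**The concern.** A platelet count below 25 per microlitre is not on the same scale as any other platelet figure in the protocol. In the aplastic anemia block, a higher grade should mean lower counts, because 8.4 defines the condition as a failure to make enough blood cells. The printed G3-4 row asks for higher ones.

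Both sets of limits stand beside a mandatory permanent discontinuation. An investigator who takes the action from Table A8 and applies the printed limits would not reach the Grade 4 stop in either block when it is due. In 8.6 that investigator would not reach the hold either.

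**Working it through.** **Inputs, all from the protocol**

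- Section 5.1, criterion 7a: platelets at least 100 x 10^9/L; ANC at least 1.5 x 10^9/L.
- Table A8, 8.6: platelet limits 100, 75, 50, 25 per microlitre.
- Table A8, 8.4: the G2 and G3-4 rows quoted above, and a G1 row that opens "G1: Nonsevere, < 0.5 polymorphonuclear cells x 10" (to the ninth, per litre).
- Table A8, 8.5: lymphopenia is "An abnormally low level of lymphocytes in PB; for adults, counts of < 1,500/mm" cubed, with "G4: < 250 PB lymphocyte count".

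**Step 1: the unit in 8.6.** One litre is 10^6 microlitres, so a value in 10^9/L is multiplied by 1000 to give cells per microlitre.

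- Criterion 7a: 100 x 10^9/L = 100,000 per microlitre. Against the printed G1 limit: 100,000 / 100 = 1000.
- Block 8.4 uses 20,000 for platelets with no unit beside it. The unit can be inferred: the G1 row gives 0.5 x 10^9/L = 500 per microlitre for neutrophils, which equals the bare ANC limit of 500 in G2. Bare counts in 8.4 are therefore per microlitre. Against the printed G4 limit in 8.6: 20,000 / 25 = 800.
- Block 8.5 counts whole cells per cubic millimetre, which is one microlitre. Its G4 limit of 250 is 250 / 25 = 10 times the platelet G4 limit. This is another cell type and shows only that the neighbouring block writes counts out in full.

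Only the figure 100 is matched directly by criterion 7a. The other three follow because all four share one printed unit.

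**Step 2: what 8.6 does to a given count**

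| Platelets per microlitre | Grade as printed | Grade with limits in 10^9/L |
|---|---|---|
| 90,000 | none | G1 |
| 60,000 | none | G2 |
| 40,000 | none | G3 |
| 20,000 | none | G4 |
| 10,000 | none | G4 |
| 100 | none | G4 |

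The first count to receive a printed grade is 99. Everything from 100 up to 100,000 per microlitre is ungraded.

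**Step 3: the signs in 8.4.** Two illustrative profiles:

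- Very severe disease (ANC 100, platelets 10,000, reticulocytes 10,000, marrow 10%). Printed G2 is met. Of the printed G3-4 conditions, 0 of 4 are met (100 > 200, 10,000 > 20,000 twice, and 10 > 25 are all false). With less-than signs, 4 of 4 are met.
- A participant at the 7a floor (ANC 1,500, platelets 100,000). Both printed G3-4 limits that 7a covers are met (1,500 > 200; 100,000 > 20,000). With less-than signs, 0 of 2 are met.

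G2 requires marrow below 25% and printed G3-4 requires marrow above 25%. Both cannot hold, so as printed a G2 case could move up to G3-4 only if the marrow recovered.

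**The case against.** The strongest reply is that the printed limits are not the operative grading rule. Sections 6.8 and 6.9.2 grade by NCI-CTCAE v5.0, Appendix 4 adds a general five-grade fallback, and the mandatory Grade 4 stop is stated without numeric limits. A platelet count of 10,000 would then be graded by CTCAE, and a clinician would see that 25 per microlitre is implausible. This stands as a limit on the harm. It does not remove the error. The default actions in Section 6.8 are for events that Appendix 5 does not cover, so Appendix 5 is where the action is found. Table A1 also departs from CTCAE grading for skin, which gives a reader some reason to take printed limits at face value. The protocol is left with two conflicting gradings at a mandatory stop.

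A second reply concerns 8.4. The joint G3-4 row does not separate G3 from G4, so correcting the signs does not by itself identify the stop, and printed G2 already holds the drug. Both points are true. A shared row also appears elsewhere in Appendix 5 and is not criticised here. But as printed, a very severe case falls outside the only row that contains the 8.4 Grade 4 stop.

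Third, the participant at the 7a floor is not a clinical case, since the row applies only once aplastic anemia has been diagnosed. That is fair. The example shows the direction of the signs, not a likely misgrading.

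Finally, the limits in CTCAE and the source guideline are not printed in these documents, so the replacement values need a source check. That also stands.

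**Conclusion.** The concern holds: both blocks are wrong as written, and the protocol's own text shows it. The 8.6 limits are 1000-fold too low, which leaves every platelet count from 100 to 100,000 per microlitre without a printed grade. In 8.4 all four G3-4 signs are reversed against the order of severity set by the G2 row.

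The conclusion rests on two assumptions: that the four 8.6 limits share one unit, and that worse aplastic anemia means lower counts, as the block's definition and G2 row imply. A fault in the text copy is unlikely, since 8.4 shows both kinds of sign and the per-microlitre unit recurs four times in 8.6; a look at the printed page would settle it.

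The risk is to the hold and stop decisions in 8.6 and to the permanent stop in 8.4. The documents do not say how many participants could be affected; few are likely. There is no effect on ORR. Nor do these limits enter the SAP: immune-related events are identified from term lists, timing, treatment and etiology (Section 15.2.3.2), and laboratory values are graded by CTCAE v5.0 (Section 15.3).

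**What to change.** Issue a clarification letter or amendment that:

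- prints the 8.6 limits as 100, 75, 50 and 25 x 10^9/L, the unit of criterion 7a;
- changes the four G3-4 signs in 8.4 to less-than, in line with the G2 row.

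Check both against CTCAE v5.0 or the source guideline before issue. As an option, repeat in Appendix 5 that the grade itself comes from NCI-CTCAE v5.0, as Section 6.8 already states.

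The cost is very small: one unit in four lines and four signs in one row, with no change to design, data collection or analysis.

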8.0 Hematologic Toxicities	
8.7 Acquired hemophilia	
Definition: Disorder caused by the development of autoantibodies (inhibitors) directed against plasma coagulation factors	
Diagnostic work-up Full blood count to assess platelet number, fibrinogen, PT, PTT, INR; the typical finding in patients with acquired hemophilia A is a prolonged activated PTT with a normal PT MRI, CT, and ultrasonography may be indicated to localize, quantify, and serially monitor the location and response of bleeding Medication review to assess for alternative causes Determination of Bethesda unit level of inhibitor	
Grading	Management
G1: Mild, 5%-40% of normal factor activity in blood, 0.05-0.4 IU/mL of whole blood	Hold ICPI and discuss resumption with patient only after taking into account the risks and benefits Administer 0.5-1 mg/kg/d prednisone Transfusion support as required Treatment of bleeding disorders with hematology consult
G2: Moderate, 1%-5% of normal factor activity in blood, 0.01- 0.05 IU/mL of whole blood	Hematology consult Administration of factor replacement (choice based on Bethesda unit of titer) Administer 1 mg/kg/d prednisone ± rituximab (dose, 375 mg/m ² weekly for 4 weeks) and/or cyclophosphamide (dose, 1-2 mg/kg/d); choice of rituximab v cyclophosphamide is patient specific and should be done with assistance of hematology consult; prednisone, rituximab, and cyclophosphamide should be given for at least 5 weeks Factors should be provided to increase level during bleeding episodes, with choice of factor based on presence or absence of inhibitor
G3-4: Severe, < 1% of normal factor activity in blood, < 0.01 IU/mL of whole blood	Permanently discontinue ICPI Admit patient Hematology consult Administration of factor replacement, choice based on Bethesda unit level of inhibitor Bypassing agents may be used (factor VII, factor VIII inhibitor bypass activity); caution should be taken in the elderly and those with coronary artery disease Prednisone 1-2 mg/kg/d (oral or IV depending on symptoms) ± rituximab (dose, 375 mg/m ² weekly for 4 weeks) and/or cyclophosphamide (dose, 1-2 mg/kg/d). Transfusion support as required for bleeding If worsening or no improvement add cyclosporine or immunosuppression/immunoabsorption
Additional considerations: The American Heart Association requires specialist clinical and laboratory expertise. Consult and/or transfer to a specialist center is often appropriate. If consultation with or transfer to a hemophilia center is not immediately possible, then investigation and treatment should be initiated while a liaison is being established. All recommendations are expert consensus based, with benefits outweighing harms, and strength of recommendations are moderate.	

Abbreviations: AE, adverse event; ANC, absolute neutrophil count; ATG, antithymocyte globulin; CBC, complete blood count; CMV, cytomegalovirus; CNS, central nervous system; CT, computed tomography; CXR, chest x-ray; DIC, disseminated intravascular coagulation; EBV, Epstein-Barr virus; ECG, electrocardiogram; ER, extended release; FE, ferritin; G, Grade; GPI, glycosylphosphatidylinositol; Hgb, hemoglobin; HHV6, human herpesvirus 6; HIV, human immunodeficiency virus; HLA, human leukocyte antigen; ICPI, immune checkpoint inhibitor; INR, international normalized ratio; irAE, immune-related adverse event; IV, intravenous; IVIG, intravenous immunoglobulin; LDH, lactate dehydrogenase; LLN, lower limit of normal; MRI, magnetic resonance imaging; NSAID, nonsteroidal anti-inflammatory drug; PB, peripheral blood; PEX, plasma ex-change; PNH, paroxysmal nocturnal hemoglobinuria; PT, prothrombin time; PTT, partial thromboplastin time; RBC, red blood cell count; TTP, thrombotic thrombocytopenic purpura.

Table A9 Management of Cardiovascular irAEs in Patients Treated With ICPis

